1.6 Study Variables

A. Independent Variables, Interventions, or Predictor Variables

The independent variables will be supplementation with SPI or GP-SPI.

B. Dependent Variables or Outcome Measures

Outcome measures are gut microbial community analyses, CMP results, urine and serum metabolites, and bacterial genes, species/strains.

1.7 Drugs/Devices/Biologics

N/A

1.8 Specimen Collection

A. Primary Specimen Collection

▪ Types of Specimens:

Version Number: 3
Protocol Number: 2018002579
PI Name: [name]
Protocol Title: The Effect of Concord grape polyphenol-soy protein isolate complex (GP-SPI) on Gut Microbiota

RESERVED FOR IRB STAMP
DO NOT MODIFY THIS SPACE

Blood samples: A blood samples will be collected by study nurse at screening visit for CMP test. If CMP is within normal ranges, subject will be enrolled in study. Blood will be collected again at baseline (day 0) and at end of study (day 11). Each blood draw will be no more than 30 mL (2 tablespoons).

Stool samples: Subjects will be provided with Omnigene®Gut OMR-200 kits or collection tubes containing 95% ethanol and/or tubes containing 50% glycerol (50% water) along with paper toilet accessories (DNA genotek, Ottawa, Canada) for easy self-collection of a pea-sized amount of fecal sample. Each participant will be instructed on use of stool collection materials.

Urine samples: Subjects will be provided with sterile collection containers (100 mL) for self-collection of urine samples on same days fecal samples are collected and asked to keep samples in 4 °C fridge until transport to the IFNH laboratory to maintain metabolite stability (20).

▪ **Annotation:**

Blood samples: CMP tests will be performed on blood samples collected at screening visit, day 0, and day 11. Targeted and untargeted metabolomics analyses will be performed on de-identified blood samples collected on days 0 and 11 from participants enrolled in study.

Stool samples: Microbial community structure will be analyzed from de-identified fecal samples as previously described (51) and used for shot gun metagenomics studies.

Urine samples: De-identified urine samples will subject for targeted and untargeted metabolomics analyses.

▪ **Transport:**

Blood samples: Blood samples collected and processed by study nurse at Clinical Academic Building will be picked up by a study staff member of [name] lab and transported to IFNH on dry ice.

Stool samples: The Omnigene®Gut OMR-200 kit allows transport and storage of stabilized DNA at ambient temperature for 60 days and 95% ethanol stabilizes samples for 8 weeks. Subjects will be asked to bring their stool samples to the IFNH laboratory as soon as possible, within 1-3 days of collection, for processing. Subjects will be asked to freeze fecal samples collected in 50% glycerol as soon as possible to minimize shifts in the microbiota, which can use glycerol as a carbon source.

Urine samples: Subjects will be instructed to keep urine samples in their 4°C fridge until transport to the IFNH laboratory to maintain metabolite stability (20).

▪ **Processing:**

Blood samples: Initial processing will be performed by study nurse. Further processing for metabolomics analysis will be performed by [name] lab research personnel working on this study.

Stool and urine samples: Processing will be performed by [name] lab research personnel working on this study.

▪ **Storage:**

Version Number: 3
Protocol Number: 2018002579
PI Name: [name]
Protocol Title: The Effect of Concord grape polyphenol-soy protein isolate complex (GP-SPI) on Gut Microbiota

*RESERVED FOR IRB STAMP
DO NOT MODIFY THIS SPACE*

Blood, stool and urine samples: Deidentified samples will be aliquoted and stored at -80 °C

De-identified specimens will be stored in locked -80°C freezers belonging to the [name] laboratory in IFNH ([name]) until analysis. Specimens may be used for future experiments which may include: 1) new sample analyses that are necessary for this study but are not listed in the current protocol and sample analyses for future studies. Consent to use stored samples for experiments is required for participation in this study. Specimens will be stored in IFNH laboratory freezer until they are no longer in a fit state for scientific analyses and may only be accessed by authorized research personnel associated with this study.

- **Disposition:**
Blood, stool, and urine samples: Specimens will be stored in IFNH laboratory freezer until they are no longer in a fit state for scientific analyses, after which they will be disposed of by incineration by REHS. Only de-identified study data will be associated with the specimens banked for future use by this PI, removing need for a repository.

B. Secondary Specimen Collection

N/A

1.9 Data Collection (Interviews, Focus Groups, or Surveys)

N/A

1.10 Timetable/Schedule of Events

	Dec 2018 - Feb 2019	Mar - Aug 2019	Sept 2019 - Mar 2020	April 2020 - ongoing
Staff/student training, research material production				
Eligibility screening, recruitment, and sample collection				
Sample processing, data generation and analyses				
Publications and results dissemination				

2.2 Research Staff Training

RESEARCH TRAINING. All investigators and research personnel will complete the Collaborative Institutional Training Initiative (CITI) training and the Lab Safety/Biological Safety/Blood Borne Pathogens Training from Rutgers Environmental Health & Safety.

The PI and RWJMS collaborators have had several meetings to develop the study. Prior to starting the study, PI will meet with study personnel to review the protocol, procedures, study forms, and each one's responsibilities going forward. Meetings will be held periodically throughout the study to review progress and make changes if necessary.

2.3 Resources Available

IFNH and CAB are equipped with conference/interview rooms for eligibility screening visits. The GP-SPI and SPI materials will be stored in freezers of Food Science pilot plant, which has space dedicated for production of food-grade study materials.

3.0 Multi-Center Research

N/A

4.0 Subject Considerations

4.1 Subject Selection and Enrollment Considerations

A. Method to Identify Potential Subjects

Flyers will be posted locally to recruit volunteers and emails will be sent to Rutgers university email lists.

B. Recruitment Details

Recruitment of the 30 participants will start in March 2019. Prospective participants will be recruited through flyers on Rutgers University campuses and email lists. Interested individuals will be asked to contact the research team by email or phone to obtain an overview of the study. We expect to recruit the majority of our participants from the New Brunswick campus of Rutgers University. We conservatively expect a recruitment rate of 3-6 participants per month over 6 months.

C. Subject Screening

Interested subjects will call in to receive further information about the study. A co-investigator/coordinator will give a brief summary of the study. If the subject requests a screening appointment, the investigator will ask for verbal consent to proceed with a list of questions. Collecting this information at this time assists in expediting the paperwork during the visit and spares ineligible subjects the inconvenience of a futile appointment.

At the screening visit, a co-investigator/coordinator will explain the study in detail to the subject. Full explanation of procedures and potential risks will be provided. The subject will have ample time to read the consent and ask questions before signing and proceeding with screening procedures. A signed copy will be given to the subject.

Inclusion Criteria:

A subject will be deemed as "healthy" and eligible for inclusion in this study if all of the following criteria are met:

1. Healthy as assessed based on a medical evaluation including a comprehensive metabolic panel (CMP) test with values in normal range, medical history, and not presently taking any medication
2. Adults between 18 and 35 years
3. BMI 18.5 - 29.9
4. Have at least one bowel movement per day
5. Capable of giving written informed consent, which includes compliance with the requirements and restrictions listed in the consent form.

Exclusion criteria:

1. History/current cancer, rheumatoid arthritis immunologic, renal, hepatic, endocrine, neurologic or heart disease, hypertension, diabetes, GI dysfunction, or CMP test results showing values outside of normal range.
2. Cannot provide written informed consent.
3. Exposure to any experimental agent or procedure within 30 days of study.
4. Pregnancy or breast-feeding
5. Taking dietary supplements
6. Current smoker or have smoked within previous 6 months
7. Taking medications regularly (prescription, over the counter, supplements etc.)

8. Treated with antibiotics during the past 6 months
9. Have an allergy to soy or grapes

4.2 Secondary Subjects

N/A

4.3 Number of Subjects

A. Total Number of Subjects

30 subjects will be enrolled after successfully passing screening. The anticipated lost to follow-up rate for this study will be 20% (i.e. 6 non-completers)

B. Total Number of Subjects If Multicenter Study

N/A

C. Feasibility

We expect to recruit the majority of our participants from the New Brunswick campus of Rutgers University. With a relatively flexible study schedule and no particularly stringent eligibility criteria, we do not anticipate difficulties in engaging interest and accommodating schedules of participants. We conservatively expect a recruitment rate of 3-6 participants per month over 6 months.

4.4 Consent Procedures

A. Consent Process

▪ Location of Consent Process

The Consent Process will take place at the New Jersey Institute for Food, Nutrition & Health

▪ Ongoing Consent

N/A

▪ Individual Roles for Researchers Involved in Consent

Principal Investigator [name], Co-Investigators [name] or [name], [name], or graduate student [name] will conduct the consent process to explain all aspects of the study and answer any questions the prospective participants may have. [name], [name], [name], [name], or [name] will sign the consent form.

▪ Consent Discussion Duration

It is expected that the consent discussion will last approximately 45 min.

▪ Coercion or Undue Influence

In order to minimize the possibility of coercion or undue influence, the consent process will not be conducted by research personnel who have any known relationship or conflict of interest with the prospective participants.

▪ Subject Understanding

Throughout the consent process the prospective participants will be encouraged to ask any questions should they feel the need to do so. The consent process will be divided into a series of small sections. Members of the research team will summarize each section, use probe questions to check for sufficient understanding before proceeding to the next section. An illustrated Study Summary will be provided to assist subject understanding of study procedures.

B. Waiver or Alteration of Consent Process

N/A

C. Documentation of Consent

▪ **Documenting Consent**

Please see attached Consent form.

▪ **Waiver of Documentation Of Consent (i.e., will not obtain subject's signature)**

N/A

4.5 Special Consent/Populations

A. Minors-Subjects Who Are Not Yet Adults

N/A

B. Wards of the State

N/A

C. Non-English-Speaking Subjects

N/A

D. Adults Unable to Consent / Cognitively Impaired Adults (for interventional studies)

N/A

4.6 Economic Burden and/or Compensation for Subjects

A. Expenses

Participants may incur expenses when they travel to our research facilities.

B. Compensation/Incentives

Subjects will receive parking for each blood draw study visit and compensated \$5 for each of 9 stool, 7 urine, and 2 blood samples delivered on days -5 through 10 and an additional \$110 on Day 11 visit for completing all requested study samples, completion of all study visits and delivery of complete digital and written food diary for a total of \$200 paid in cash. One missed or incomplete visit will result in only \$5 for each blood, urine and stool sample delivered on Days -5 through 10.

C. Compensation Documentation

Each participant will be asked to sign a form confirming receipt of stated amount of compensation at end of their participation in the study. See page 3 of "**Log of Study Visits & Receivables**" form; once signed this page will be moved to separate binder and kept in a separate locked cabinet.

4.7 Risks of Harm/Potential for Benefits to Subjects

A. Description of Risks of Harm to Subjects

▪ **Reasonably Foreseeable Risks of Harm**

Study Supplement – there are no known risks to ingesting the study supplement. To minimize the risk of an allergic reaction the study excludes persons allergic to soy or grapes.

Blood Sampling – may cause a bruise or bleeding at the site. Infection at the site is rare.

A total of 65 mL (~ 4 Tablespoons) will be drawn during the course of the study. Healthy subjects can tolerate this blood loss without any side effects.

Urine and Stool collection – There is risk of discomfort with sample collection and storage.

These risks are considered minimal and are addressed in the protocol and consent form. To minimize expected risk, study staff will communicate with subjects during intervention period and do a final follow up by phone or email 2 - 3 weeks after end of intervention.

- **Risk of Harm from an Intervention on a Subject with an Existing Condition**

N/A

- **Other Foreseeable Risks of Harm**

All efforts will be made to keep personal information in subject research record confidential, but total confidentiality cannot be guaranteed.

- **Observation and Sensitive Information**

N/A

B. Procedures which Risk Harm to Embryo, Fetus, and/or Pregnant Subjects

Soy protein and dietary polyphenols are often consumed as part of a normal diet; however, in case of pregnancy within the 15-day study period, the risk of GP-SPI to a newly formed embryo/fetus is uncertain. This study will not include pregnant subjects and a urine-based pregnancy test will be performed to confirm inclusion of only non-pregnant participants.

C. Risks of Harm to Non-Subjects

N/A

D. Assessment of Social Behavior Considerations

N/A

E. Minimizing Risks of Harm

All procedures will be explained to subjects at the time of obtaining consent and subjects will be encouraged to ask questions about any concerns throughout the study. Every effort will be made to maintain subject confidentiality.

- **Certificate of Confidentiality**

This study is partially funded by NIH-NCCIH therefore a Certificate of Confidentiality is automatically issued to protect data collected.

- **Provisions to Protect the Privacy Interests of Subjects**

Should any participants desire not to interact with or provide personal information to specific members of the research team, they may report such a need to the Principal Investigator and the arrangement of the research personnel will be adjusted accordingly. Participants will not be required to provide a reason if they desire not to do so. Should changing of the research personnel is not possible, the Principal Investigator will discuss with the participants about alternative solutions.

In order to ensure the protection of personal health information of the participants, there will be no identifiable information on any of the data collection instruments. Each participant will be assigned a unique identification code. A master code identifier which links the identification code and personal information (name, date of birth and contact information) will be maintained separately from the study data. Only the Principal Investigator and approved research personnel who have a specific need for identifiable information will have access (e.g. their primary physician, research student/staff to schedule appointments). All data and materials

collected during this study are for research purposes only, and the data will be kept in strict confidence. No information will be given to anyone without permission from the participants.

F. Potential Benefits to Subjects

There are no direct benefits for the subjects. Subjects will receive a copy of results from health assessment blood tests, if abnormal they will be encouraged to see their doctor.

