1.3 Research Design and Methods

Overview

This is a pilot time course study to characterize the effect of GP-SPI on the gut (i.e. fecal) bacterial community of healthy subjects. Following screening, enrolled subjects will washout of PAC-rich foods for 5 days while also consuming SPI. Subjects will then consume GP-SPI over a 10-day supplementation period. Fecal, urine, and blood samples will be collected. Comprehensive metabolic panel (CMP) tests performed before and after the GP-SPI supplementation period will monitor liver and kidney health. Using deidentified fecal, urine, and blood samples collected from time course study a MWAS study (funded by R01 AT010242-01) will be performed.

Successful completion of this pilot study will yield data that will inform the design of a follow-up placebo-controlled intervention study, which will be described in a separate clinical protocol that will be submitted to IRB for approval.

A. Research Procedures

[figure not shown]

Figure 1. Clinical Study Design

Location

Screening and out-patient visits will take place in the Surgery Clinic in the Clinical Academic Building (CAB) or Surgery Department (MEB 5) and NJ Institute of Food Nutrition and Health (IFNH).

Recruitment

Prospective participants will be recruited through flyers posted locally on Rutgers University campuses and sent to university email lists (**Flyer** attached). Interested subjects will call in or email to receive further information about the study. A member of the study team will give a brief summary of the study. If the subject requests a screening appointment, the investigator will ask for verbal consent to proceed with a list

of questions (**Telephone Script** attached). Collecting this information at this time assists in expediting the paperwork during the visit and spares ineligible subjects the inconvenience of a futile appointment.

Eligibility Screening

At the screening visit (at IFNH), a member of the study team will explain the study in detail to the subject. Full explanation of study procedures and potential risks will be provided. The subject will have ample time to read the Consent and ask questions before signing and proceeding with screening procedures. A signed copy of Consent form (form attached) will be given to the subject.

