After consent a participant ID will be assigned to subject. Demographics, medical history, height, and weight (**Demographics** and **Medical History** forms attached) will be recorded for each subject. Females will be given a urine-based pregnancy test onsite and result will be recorded. If inclusion criteria are met at this time, subject will be asked to schedule a visit at CAB with study nurses for a blood draw to perform CMP screening test. If CMP results are within normal range the subject will be enrolled and return to IFNH to receive study materials needed for participation in the study. If any CMP values are outside normal ranges subject will be advised that they do not fulfill all eligibility criteria, they will be given a copy of their CMP results, and if necessary, advised to see their primary care provider. All screened subjects will be documented on **Screening and Enrollment Log** (attached).

The final selection will be contingent upon the individuals meeting all eligibility criteria and deemed capable of complying with the study protocol.

Study Procedures

- Thirty subjects will be enrolled.
- **Food List:** Participants will maintain their usual diet except for a provided list of PAC-rich foods that they will be asked to abstain from for a 5-day wash-out period and during the 10-day intervention. The Food List is provided below. The goal is to have GP-SPI as the main/only source of PAC in the diet for the study period.
- **Wash-out and SPI (Day -5 through -1):** On day -5 (pre-baseline) before any supplementation, each subject will collect their fecal and urine sample. Each subject will then consume SPI twice a day (provided as pre-weighed packets of 20 g) during a 5-day wash-out period (days -5, -4, -3, -2, and -1). Subjects will be instructed to mix each packet of SPI in 250 mL of water or in a smoothie (recipe example below will be provided) using allowed foods as detailed in instructions and consume once in the morning before breakfast and once in the evening before dinner.

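### The only pregnancy test described is at the first screening visit, with no limit on its age, so it cannot support the Section 4.7 assurance at enrolment or at first exposure

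*Combined protocol and SAP*

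**What the plan says.** Section 4.7 B gives the reason for testing: "in case of pregnancy within the 15-day study period, the risk of GP-SPI to a newly formed embryo/fetus is uncertain". It then gives the assurance: "This study will not include pregnant subjects and a urine-based pregnancy test will be performed to confirm inclusion of only non-pregnant participants". Exclusion criterion 4 in Section 4.1 C reads "Pregnancy or breast-feeding" and carries no test date or time limit.

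Section 1.3, under Eligibility Screening, sets out the sequence:

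- The first visit is at IFNH: "At the screening visit (at IFNH), a member of the study team will explain the study in detail to the subject".
- After consent at that visit, "Females will be given a urine-based pregnancy test onsite and result will be recorded".
- If the inclusion criteria are met so far, the "subject will be asked to schedule a visit at CAB with study nurses for a blood draw to perform CMP screening test".
- Only if the panel (CMP) is normal, "the subject will be enrolled and return to IFNH to receive study materials needed for participation in the study".

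Table 1 has one mark for the urine pregnancy test and one for the inclusion and exclusion check, both in the Screen column. Section 1.8 differs from Section 1.3 in one respect: it has the study nurse take the panel sample at the screening visit, as if screening were a single attendance.

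**The concern.** A pregnancy test shows status on the day it is done. The plan presents this one as confirming who is included, but enrolment comes later, after a laboratory result, and exposure later still. The plan itself regards exposure in early pregnancy as a matter of uncertain risk. It enrols adults aged 18 to 35 and expects no direct benefit to them (Section 4.7 F), so a stated safeguard should do what the text says it does.

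The matter is one of participant safety and internal consistency. It touches no endpoint, estimate or error rate.

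**Working it through.** The plan has no figure to reproduce. The check is to order the steps and count days.

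**Order of steps (Section 1.3 and Table 1)**

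1. IFNH screening visit: consent, history, urine pregnancy test.
2. CAB visit: blood draw for the panel.
3. Panel result; enrolment if normal.
4. Return to IFNH for study materials.
5. Day -5: first SPI packet.
6. Day 0: blood draw at CAB, samples delivered to IFNH, GP-SPI packets collected. No pregnancy test is listed.
7. Day 1: first GP-SPI packet. Day 10: last.

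Two attendances (steps 2 and 4) and a laboratory turnaround separate the test from the first SPI packet. The Day 0 attendance also precedes the first GP-SPI packet. None of the intervals between steps 1 and 5 has a stated limit. Other exclusions do carry windows: 30 days for experimental agents and 6 months for antibiotics and for smoking.

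**Age of the result**

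Let g be the number of days from the test to Day -5, with g at least 0. The documents do not state it.

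- At the first SPI packet: g.
- At the first GP-SPI packet: g + (1 − (−5)) = g + 6.
- On the last GP-SPI day: g + (10 − (−5)) = g + 15.

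| g (days) | First GP-SPI packet | Last GP-SPI day |
|---|---|---|
| 0 (lower bound) | 6 | 15 |
| 7 (assumed) | 13 | 22 |
| 14 (assumed) | 20 | 29 |
| 28 (assumed) | 34 | 43 |

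Only the first row follows from the documents. The others are illustrations.

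**Exposure**

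Two packets a day for 10 days is 2 × 10 = 20 GP-SPI packets. The 2 × 5 = 10 SPI packets are not counted, because Section 4.7 B calls only the risk of GP-SPI uncertain.

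**Single-visit reading of Section 1.8**

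If the panel were drawn at the same attendance as the pregnancy test, step 2 would merge with step 1. The panel result, enrolment and collection of materials would still follow, g would still be unlimited, and the 6 and 15 days would be unchanged.

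**The case against.** The case against has several parts.

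- **The rules already exclude pregnancy.** A reader might infer that a woman who conceives after screening could be given product with every written rule satisfied. The documents do not support that. Exclusion criterion 4 has no time limit, and Section 1.3 makes final selection depend on meeting all criteria, so a woman pregnant at enrolment would breach it. The gap is in detection, not in the rule.
- **The assurance may be only an entry check.** On this reading Section 4.7 promises no more than a test at entry, and one is done. This stands in part, since the test does show status on screening day. But enrolment follows the panel result, so the test precedes even entry.
- **A later test has the same weakness.** No test before dosing excludes a very early pregnancy or conception during supplementation, and Section 4.7 B expressly mentions pregnancy within the study period. This stands: re-timing shortens the interval but does not close it.
- **Other safeguards may exist.** A reader might infer that this test is the only one. That cannot be established. The consent form, telephone script and medical history form are attachments not available here, and inclusion criterion 5 relies on restrictions in the consent form. Section 4.7 A also provides for staff contact during the intervention and a follow-up 2 to 3 weeks afterwards.
- **The absolute risk may be small.** Section 4.7 describes soy protein and polyphenols as ordinary dietary components, and Section 6.3 C places the intake within the range of a total diet. This bears on priority. It does not reconcile the assurance with the timing.

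**Conclusion.** The point holds for detection. The available text describes one test, done before enrolment, with no limit on its age, and Section 4.7 B offers it as confirming that only non-pregnant participants are included. That is not secured at enrolment or at first exposure. The result is at least 6 days old at the first GP-SPI packet and at least 15 on the last GP-SPI day, with no upper limit on either. A participant whose pregnancy went undetected could take up to 20 GP-SPI packets.

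The minimum ages follow from the schedule alone; anything longer depends on an assumed g. The conclusion is confined to the text available. The documents do not show that any pregnant participant would be enrolled.

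**What to change.** Reconcile Section 1.3 (Eligibility Screening), Table 1, Section 1.8 and Section 4.7 B so that they describe one sequence and one test timing that supports the stated assurance. Two ways would serve:

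- Schedule the planned urine test at the existing IFNH visit where materials are collected, with or without keeping the screening test. The interval from that visit to Day -5 should also be stated, since it is now open.
- Keep the test at screening and state a maximum number of days, W, from the test to Day -5. The result would then be at most W + 6 days old at the first GP-SPI packet and W + 15 on the last GP-SPI day. The choice of W is the sponsor's.

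In either case, limit the wording of Section 4.7 B to what the chosen timing can show, and acknowledge that very early pregnancy and conception during supplementation are not excluded. State in Sections 1.3 and 1.8 whether screening is one attendance or more. Action on a result is left to the investigators under exclusion criterion 4.

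The cost is a minor amendment with no new visit. If the screening test is kept as well, it adds at most one strip per woman, so no more than 30 strips for the 30 participants to be enrolled.
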